9.3 ANALYSIS SETS

The analysis sets for evaluating the efficacy, safety, and pharmacokinetics of etokimab are defined in Table 2.

Table 2. Analysis Sets

Analysis Set	Description
Safety Analysis Set	The safety analysis set will include all randomized subjects who receive 1 dose of etokimab or placebo. The safety analysis set will be used for all safety analyses. Subjects will be analyzed as treated.
Full Analysis Set	The full analysis set (FAS) will include all randomized subjects who receive 1 dose of etokimab or placebo and have baseline and at least 1 post baseline NPS and/or SNOT-22 scores up to Week 16. The full analysis set will be used for all efficacy analyses. Subjects will be analyzed as randomized.
PP Analysis Set	The PP (Per Protocol) analysis set will include all subjects in the FAS analysis set who do not have major protocol violations that would affect the evaluation of the primary efficacy endpoints.
PK Analysis Set	The PK analysis set will include all subjects in the safety analysis set who have at least one quantifiable postdose PK sample available and who do not have events or protocol deviations or events with the potential to affect PK concentrations. The PK analysis set will be used for all PK analyses.

Abbreviations: FAS = Full analysis set, PP = Per protocol, PK = Pharmacokinetics.

9.4 STATISTICAL ANALYSES

9.4.1 GENERAL APPROACH

The final statistical analysis will be performed after all reportable data have been collected, queries resolved, and the database locked. The Statistical Analysis Plan (SAP) will be developed and finalized before the database lock and will provide full details of all statistical analyses, including procedures for accounting for missing, unused, and spurious data. This section summarizes the planned statistical analyses of the primary and secondary endpoints.

The statistical analyses will be performed using statistical analysis system (SAS®) version 9.4 or higher if available. All details regarding the statistical analyses and the preparation of tables, listings and figures will be described in the SAP.

In general, continuous variables will be summarized with descriptive statistics including n, mean, SD, median, minimum, and maximum. Categorical variables will be summarized by the number and percentage of subjects in the relevant analysis set and treatment group falling into each category.

Unless otherwise specified, "baseline" is defined as the last observed value of the parameter of interest prior to the first intake of study drug (this includes unscheduled visits). For numerical variables, change from baseline will be calculated as the difference between the value of interest and the corresponding baseline value.

Unless otherwise specified, all formal statistical tests will be 2-sided at the 5% significance level. Point estimates will be accompanied with 2-sided 95% confidence intervals (CIs), where applicable. In the case of normality assumption violations, appropriate nonparametric methods will be used for analysis.

All data will be presented in by subject and treatment listings.

9.4.2 EFFICACY ANALYSES

A summary of the efficacy endpoints (co-primary, secondary, and exploratory) and the statistical methods that will be used to analyze these endpoints is provided in Table 3. The co-primary efficacy analyses will be performed on the FAS. Additionally, the co-primary efficacy analyses will be repeated on the PP Analysis set.

Table 3. Efficacy Analyses

Endpoint	Statistical Analysis Methods	
Co-Primary Efficacy:		
Change from baseline to Week 16 in bilateral endoscopic NPS	General linear mixed effects model with repeated measures (MMRM) including the change from baseline in NPS as dependent variable; treatment group, stratification factor, time (Weeks 4, 8, 12, and 16), treatment by stratification factor, and treatment by time interaction as fixed effect factors; baseline NPS score as covariate; and subject as random effect.	
Change from baseline to Week 16 in SNOT-22 scores	MMRM as above for NPS will be applied for SNOT- 22 score.	
Secondary Efficacy:		
Time to first response (≥1 point reduction in NPS)	Log rank test to compare the time to first response for the treatments	
Responder analysis: response defined as a reduction of ≥1point from baseline to Week 16 in NPS	Logistic regression modeling the response as dependent variable, treatment, baseline NPS, and asthma comorbidity as covariates	
Responder analysis response defined as a reduction of ≥12 points from baseline to Week 16 in SNOT-22	Logistic regression modeling the response as dependent variable, treatment, baseline SNOT-22 score, and asthma comorbidity as covariates	
Change from baseline to Week 16 in UPSIT	MMRM proposed for NPS will be applied for UPSIT.	

Endpoint	Statistical Analysis Methods	
Exploratory Efficacy		
Change from baseline to Week 16 in sinus opacification as assessed by CT scan using Lund-Mackay score	Analysis of covariance (ANCOVA) modeling the change from baseline in Lund-MacKay score at Week 16 as dependent variable; baseline Lund-MacKay score as covariate; and treatment as a factor	
Change from baseline to Week 16 in AM NPIF	MMRM, including the change from baseline in AM NPIF as the dependent variable; treatment group, stratification factor, time (Weeks 4, 8, 12, and 16), treatment by stratification factor, and treatment by time interaction as fixed effect factors; baseline AM NPIF score as covariate; and subject as a random effect	
Change from baseline to Week 16 in PM NPIF	MMRM, including the change from baseline in PM NPIF as the dependent variable; treatment group, stratification factor, time (Weeks 4, 8, 12, and 16), treatment by stratification factor, and treatment by time interaction as fixed effect factors; baseline PM NPIF score as covariate; and subject as a random effect	
Change from baseline to Week 16 in bilateral endoscopic NPS in subjects with comorbid asthma	MMRM including the change from baseline in NPS as dependent variable; treatment group, time (Weeks 4, 8, 12, and 16), and treatment by time interaction as fixed effect factors; baseline NPS score as covariate; and subject as random effect	
Change from baseline to Week 16 in SNOT-22 in subjects with comorbid asthma	MMRM as above for NPS will be applied for SNOT- 22 score	
Change from baseline to Week 16 in the percent of 3-dimentional volumetric maxillary sinus occupied by disease (%VMSOD) as assessed by CT scan	Analysis of covariance (ANCOVA) modeling the change from baseline in %VMSOD score at Week 16 as dependent variable; baseline %VMSOD score as covariate; and treatment as a factor	
Change from baseline to Week 16 in SF-36 physical component summary (PCS)	MMRM including the change from baseline in SF-36 PCS score as dependent variable; treatment group, stratification factor, time (Weeks 4, 8, 12, and 16), treatment by stratification factor, and treatment by time interaction as fixed effect factors; baseline SF-36 PCS score as covariate; and subject as a random effect	
Change from baseline to Week 16 in SF-36 mental component summary (MCS)	MMRM as above for SF-36 PCS will be applied for SF-36 MCS	

Endpoint	Statistical Analysis Methods
Change from baseline to Week 16 in EQ-5D index score	MMRM including the change from baseline in EQ-5D index score as dependent variable; treatment group, stratification factor, time (Weeks 4, 8, 12, and 16), treatment by stratification factor, and treatment by time interaction as fixed effect factors; baseline EQ-5D index score as covariate; and subject as a random effect
Change from baseline to Month 4 in VAS	MMRM including the change from baseline in VAS score as dependent variable; treatment group, stratification factor, time (Months 1, 2, 3, and 4), treatment by stratification factor, and treatment by time interaction as fixed effect factors; baseline VAS score as covariate; and subject as a random effect
Number of nocturnal awakenings (in subgroup with comorbid asthma)	Cochran Mantel-Hanszel statistics testing the row mean scores differ between treatment groups at each visit
Change from baseline to Week 16 in FEV ₁ (overall and in subgroup with asthma)	MMRM including the change from baseline in FEV ₁ score as dependent variable; treatment group, stratification factor, time (Weeks 4, 8, 12, and 16), treatment by stratification factor, and treatment by time interaction as fixed effect factors; baseline FEV ₁ score as covariate; and subject as a random effect
Change from baseline to Week 16 in % predicted FEV ₁ (overall and in subgroup with asthma)	MMRM including the change from baseline in %predicted FEV ₁ score as dependent variable; treatment group, stratification factor, time (Weeks 4, 8, 12, and 16), treatment by stratification factor, and treatment by time interaction as fixed effect factors; baseline %predicted FEV ₁ score as covariate; and subject as a random effect
Change from baseline to Week 16 in ACQ-7 total score in subjects with comorbid asthma	MMRM including the change from baseline in ACQ-7 score (mean of the responses to all 7 questions) as dependent variable; treatment group, time (Weeks 4, 8, 12, and 16), and treatment by time interaction as fixed effect factors; baseline ACQ-7 score as covariate; and subject as a random effect

Endpoint	Statistical Analysis Methods
Change from baseline to Week 16 in blood eosinophil count	MMRM modeling the change from baseline in blood eosinophil count at Week 16 as dependent variable; treatment group, stratification factor, time (Weeks 4, 8, 12, and 16), treatment by stratification factor, and treatment by time interaction as fixed effect factors; baseline blood eosinophil count as covariate; and subject as a random effect
Time to study treatment discontinuation	Log rank test to compare the time to study treatment discontinuation
Incidence of treatment discontinuation due to need for OCS or nasal polyp surgery	Fisher's exact test comparing the proportion of subjects with treatment discontinuation due to need for OCS or nasal polyp surgery
Nasal Polyp Resource Questionnaire at each visit	Descriptive statistics (number, percentage) to be provided per questionnaire item per visit

Abbreviations: ANCOVA = analysis of covariance, CT = computed tomography, EOT = end of treatment, EQ-5D = EuroQoL-5D Scale, MMRM = mixed effects model with repeated measures, MPS = mental component summary, NPIF = nasal peak inspiratory flow, NPS = Nasal Polyp Score, PCS = physical component summary, SF-36 = Short Form 36 Health Survey, SNOT-22 = Sino-Nasal Outcome Test, UPSIT = University of Pennsylvania Smell Identification Test, VMSOD = volumetric maxillary sinus occupied by disease

Statistical significance for the co-primary efficacy endpoints will be declared if both p-values for the tests of the individual hypotheses, as described below, are < 0.05.

9.4.2.1.1 FIRST CO-PRIMARY ENDPOINT

The first co-primary endpoint is the change from Baseline to Week 16 in bilateral endoscopic NPS while on treatment.

Baseline endoscopic NPS is the sum of the left and right nasal polyposis score at the randomization visit. The NPS is also measured every 4 weeks during treatment and at end of treatment (Week 16). A general linear MMRM using change from baseline in NPS scores at Weeks 4, 8, 12, and 16 as response, stratification factor, treatment group as fixed effect (3 levels), treatment by stratification factor, and treatment by time interaction as fixed effects, Baseline (Day 1) NPS score as fixed continuous covariate, and subject as a random effect, will be used to obtain least squares means at EOT, to compare the etokimab treatment arms with the placebo arm.

No imputation of data for missing data due to treatment discontinuation will be implemented in the primary analysis. Comparison of the treatment arms will be based on the Week 16 least squares means of the treatment arms. An unstructured covariance matrix will be assumed and estimated in order to obtain associated standard errors for least squares means and to carry out the treatment comparisons. In case of convergence problems for the maximum likelihood estimates, other covariance structures with fewer parameters may be sought from the range of options provided in SAS PROCEDURE MIXED.

Comparison of each treatment arm with placebo will be based on the Week 16 least squares means obtained from the MMRM, where missing data due to treatment discontinuation are regarded as missing at random. Testing will be conducted in a hierarchical manner such that the comparison of the etokimab every 4 weeks treatment arm versus placebo will be conducted first. If the results of the comparison of the etokimab every 4 weeks treatment arm versus placebo are statistically significant, the etokimab every 8 weeks treatment arm will be compared to placebo. The p-value for the comparison will be obtained and compared to the significance level of 5%. An associated 2-sided 95% confidence interval will be obtained for the active minus placebo change from baseline to week 16 in the NPS for each treatment arm tested. No further adjustment will be made for testing each dosing regimen with placebo.

In order to assess the impact of missing data due to treatment discontinuation, a sensitivity analysis may be performed where their data after dropout will be imputed using multiple imputation and the statistical analysis using MMRM will be repeated. Another sensitivity analysis may be performed where observed values of the NPS score obtained during study but after treatment discontinuation, if available, will be used. The MMRM model will be utilized where the treatment discontinuations are regarded as not missing at random (NMAR). Full details will be specified in the SAP.

9.4.2.1.2 SECOND CO-PRIMARY ENDPOINT

The second co-primary endpoint is the change from Baseline to Week 16 in SNOT-22 scores.

An MMRM as described above for NPS, using the Baseline (Day 1) SNOT-22 score as fixed covariate, will be utilized for the SNOT-22.

Baseline endoscopic NPS is the sum of the left and right nasal polyposis score at the randomization visit.

Comparison of each treatment arm with placebo will be based on the Week 16 least squares means obtained from the MMRM. The p-value for the comparison will be obtained and compared to the significance level of 5%. An associated 2-sided 95% CI will be obtained for the active minus placebo change from baseline to Week 16 in the SNOT-22. No further adjustment will be made for testing each dosing regimen with placebo.

In order to assess the impact of missing data due to treatment discontinuation, a sensitivity analysis may be performed where their data after treatment discontinuation will be imputed using multiple imputation and the statistical analysis using MMRM will be repeated. Another sensitivity analysis may be performed where observed values of the SNOT-22 score obtained during study but after treatment discontinuation, if available, will be used. The MMRM model will be utilized where the treatment discontinuations are regarded as NMAR. Full details will be specified in the SAP.

9.4.2.2 ANALYSIS OF THE SECONDARY AND EXPLORATORY ENDPOINT(S)

Analysis of secondary efficacy endpoints will be performed in a hierarchical order as listed in Section 3 to adjust for statistical multiplicity. More details for multiplicity adjustment will be described in SAP.

For the secondary PK endpoints, primary PK parameters of CL/F and volume of distribution will be estimated by population PK modeling from ANB020 serum concentrations after SC administrations. Secondary PK parameters of AUC_{tau}, C_{max}, t_{max}, for the first dose and AUC_{tau}, C_{max}, t_{max} and T_{1/2} for the last dose will also be calculated for ANB020 after SC administrations, where possible, using a Bayesian post-hoc estimation approach based on the aforementioned population PK model. Other parameters may be evaluated, if needed. The PK parameters will be listed and summarized using appropriate descriptive statistics. Pharmacokinetic concentration data collected from the study may be included in a population PK based (meta) analysis, using non-linear mixed effects modeling. The data from this study may be combined with data collected from other studies for population PK model development. A covariate screen of subject specific factors (eg, demographic and clinical characteristics) will be included in the analyses. Any population PK analysis plan will be described in detail in a pharmacometric analysis plan.

All secondary and exploratory efficacy analyses will be performed on the FAS. Table 3 includes a summary of the statistical methods to be used in analyzing efficacy endpoints (co-primary, secondary, and exploratory). Full details of statistical analysis for all secondary and exploratory endpoints will be provided in the SAP.

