To assess improvement in Quality of Life (QoL) in subjects with CRSwNP treated with etokimab compared to placebo following a 16-week treatment period	 QoL: 36-item Short Form Health Survey (SF-36) European QoL scale (EQ-5D) Patient-related rhinosinusitis symptoms severity using a visual analogue scale (VAS) Number of nocturnal awakenings 	To assess the effect of etokimab on the patients' symptoms and quality of life
To assess other effects of etokimab compared to placebo in subjects with CRSwNP following a 16-week treatment period	 Percent change from baseline to Week 16 in sinus opacification as assessed by CT scan using Lund-Mackay score Change from baseline to Week 16 in nasal peak inspiratory flow (NPIF) Change from baseline to Week 16 in NPS in subjects with comorbid asthma Change from baseline to Week 16 in Sino-Nasal Outcome Test (SNOT-22) scores in subjects with comorbid asthma Percent change from baseline to Week 16 in 3-dimensional volumetric measurement of the maxillary sinus as assessed by CT scan Change from baseline to Week 16 in forced expiratory volume (FEV₁) (overall and in subgroup with asthma) Change from baseline to Week 16 in FEV₁ percent of predicted (overall and in subgroup with asthma) 7-Item Asthma Control Questionnaire (ACQ-7) in asthma subgroup Reduction of eosinophils (blood eosinophil count) from baseline (Day 1 pre-dose) to Week 16 	All other efficacy endpoints have been recategorized as exploratory endpoints Additional measures of treatment response are established methods to characterize the clinical impact of treatment Patient-reported outcomes specific to CRSwNP provide additional evidence to support the physician assessment of outcome

OBJECTIVES	ENDPOINTS	JUSTIFICATION FOR ENDPOINTS
	 Time to study treatment discontinuation Incidence of treatment discontinuation due to need for oral corticosteroids (OCS) or nasal polyp surgery Change in Nasal Polyp Resource Questionnaire from baseline to Week 16 	

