5.3. Full Analysis Set

The Full Analysis Set (FAS) will include all randomized subjects who receive at least 1 dose of etokimab or placebo and have baseline and at least 1 post baseline NPS and/or SNOT-22 scores up to Week 16. Subjects will be analyzed according to randomized treatment. Unless specified otherwise, this set will be also used for subject listings and summaries for all efficacy analyses.

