8.3.9. Time to Treatment Discontinuation

Time to treatment discontinuation will be calculated as the number of days from the randomization date to the date the subject discontinued study medication. This variable is censored for subjects who did not discontinue study medication and completed the treatment. The censoring date is the date of treatment completion.

The time to discontinuation will be analyzed using methods for survival data. Kaplan-Meier plots of the estimate of survivor function for the 3 treatment arms will be provided in one graph. A log-rank test will be used to compare each etokimab dose group with the Placebo group.

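### The two treatment-discontinuation endpoints are assigned to the FAS, so a dosed subject who stops before Week 4 and never provides a score drops out of an analysis of stopping; a minor point with a one-sentence fix

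*Protocol*

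**What the plan says.** Protocol Section 3 lists both endpoints as exploratory: "Time to study treatment discontinuation" and "Incidence of treatment discontinuation due to need for oral corticosteroids (OCS) or nasal polyp surgery". Table 3 (Protocol 9.4.2) places them under exploratory efficacy. The first is assigned a "Log rank test to compare the time to study treatment discontinuation" and the second a Fisher's exact test.

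Protocol 9.4.2.2 fixes the analysis set: "All secondary and exploratory efficacy analyses will be performed on the FAS". Under Protocol 9.3, FAS subjects must be randomised, be dosed and "have baseline and at least 1 post baseline NPS and/or SNOT-22 scores up to Week 16". SAP 5.3 repeats the definition and adds: "Unless specified otherwise, this set will be also used for subject listings and summaries for all efficacy analyses".

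SAP 8.3.9 sets the clock: "Time to treatment discontinuation will be calculated as the number of days from the randomization date to the date the subject discontinued study medication". Neither it nor SAP 8.3.10 names an analysis set or a denominator. SAP Section 12, on departures from the protocol, does not mention the point.

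**The concern.** A score requirement makes sense for an endpoint computed from scores. It does nothing for an endpoint that records whether and when treatment stopped, which is known from the discontinuation date and reason. Here it also conditions the analysis on something that happens after randomisation and is related to the outcome. Time runs from randomisation, but a subject enters the risk set only if a score is obtained later, and someone who stops very early is the person most likely not to provide one.

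Any subjects lost this way would make the early part of the Kaplan-Meier curve too flat and the incidence too low in that arm. If the arms lose different numbers, the log-rank and Fisher comparisons shift as well.

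**Working it through.** **Step 1: who can be left out.** The Schedule of Activities has no endoscopy or SNOT-22 at the Day 5 visit, so the first scheduled post-baseline score is at Week 4 (Day 29). A subject who stops before then can still enter the FAS in three ways:

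- An early termination visit. Protocol 7.1 asks for it within 30 days of last dose. The Week 24/EOS/ETV column of the Schedule includes endoscopy and SNOT-22, and SAP Table 2a maps Days 2 to 42 to Week 4.
- An unscheduled assessment, mapped in the same way (SAP 6.4).
- A continued study visit, which Protocol 7.1 encourages.

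One score of either kind is enough. Exclusion therefore needs early stopping and no score by any of these routes. The documents foresee how that can happen: loss to follow-up (Protocol 7.3), withdrawal from evaluations (Protocol 9.4.2.3), and follow-up by telephone after stopping (SAP 8.1.1.1), which cannot yield an endoscopic score.

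**Step 2: the plan's own figure.** The documents give no rate for either endpoint. The nearest figure is the 18% for dropouts and missing data in Protocol 9.2. It reproduces the planned arm size: 27 / (1 − 0.18) = 32.9, rounded up to 33. I use 0.18 × 33 = 5.9, about 6 per arm, as an assumed number of treatment discontinuations. The 18% is not defined that way, and it says nothing specific about OCS or surgery.

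**Step 3: effect within an arm.** With D true events among N subjects, k of them unscored, the FAS incidence is (D − k) / (N − k). For D = 6 and N = 33:

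| k unscored | FAS incidence |
|---|---|
| 0 | 6/33 = 18.2% |
| 1 | 5/32 = 15.6% |
| 2 | 4/31 = 12.9% |
| 3 | 3/30 = 10.0% |

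If stopping were uniform over 16 weeks, 6 × 4/16 = 1.5 events per arm would fall before Week 4. If 25% to 50% of those (assumed) gave no score, k would average 0.375 to 0.75, and incidence would be 5.625/32.625 = 17.2% to 5.25/32.25 = 16.3%.

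**Step 4: effect between arms.** These are constructed cases, with two-sided Fisher p-values:

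- Placebo 8/33 against active 1/33: p = 0.027. Removing 2 placebo events (6/31) gives p = 0.050; removing 3 (5/30) gives p = 0.094.
- Equal true counts of 6/33, with 3 events removed from one arm only: 6/33 against 3/30, p = 0.48. The apparent 8.2-point difference (18.2% − 10.0%) comes entirely from the analysis set.

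**The case against.** The strongest reply is that the plan already brings most early stoppers into the FAS. The early termination visit collects both scores, and SAP 6.4 maps it to an analysis visit. Subjects given systemic rescue are directed to the same visit (Protocol 6.5.1), so the OCS endpoint is covered too. After Day 1 the first dose that can be missed is at Week 4, and endoscopy precedes dosing there (Protocol 8.1.1), so a subject who attends and declines the injection is still scored. This stands, and it is why the expected loss is small.

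It also disposes of a reading that a reader might infer: that every discontinuation before Week 4 is deleted, or that a subject must remain until about Day 29 to count. An early termination score before Day 29 is enough.

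A second tempting reading is that the treatment comparison is materially distorted. One can construct placebo 8/33 against active 4/33, a 12.1-point difference, shrinking to 5/30 − 4/33 = 4.5 points. That needs 3 placebo events before Week 4, all unscored, and none on active. Uniform stopping would give 8 × 4/16 = 2. The conclusion does not change either (Fisher p = 0.34 and 0.73).

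Third, other outputs partly cover these subjects. SAP 7.1 tabulates disposition with reasons, using randomised subjects as the denominator. SAP 10.2.1 tabulates adverse events that led to permanently stopping study drug, on the Safety Analysis Set. Both are descriptive. The first concerns leaving the study rather than treatment, and the second misses stopping for lack of effect. They soften the point without replacing the two tests.

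**Conclusion.** The point holds as a minor one. The assignment to the FAS is explicit in Protocol 9.4.2.2 and not overridden in the SAP text, and for these two endpoints it can only remove events within an arm, never add them. The direction between arms cannot be determined in advance.

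The size rests on k, the number of unscored early discontinuations, which the documents do not give. The Step 3 table assumes 6 events per arm of 33 and k from 0 to 3. The lower end is more plausible given the early termination visit, and at k = 0 nothing changes.

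A reader might infer that these endpoints carry the study's evidence on treatment failure. The documents do not say so: Section 3 lists them among other exploratory effects, outside the secondary testing hierarchy in SAP 8.2. Primary and secondary inference and the overall alpha are unaffected.

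**What to change.** In SAP 8.3.9 and 8.3.10, and in Protocol 9.4.2.2 with Table 3, state that these two endpoints are analysed in all randomised subjects who received study drug, grouped as randomised, and that the FAS applies to score-based endpoints. The grouping should be written out, because the Safety Analysis Set contains the same subjects but groups them by treatment received. Restricting to dosed subjects adds little conditioning, since SAP 6.2.2 expects the first dose on the day of randomisation.

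The cost is one sentence in each place. The randomisation date, stopping date and reason are already needed for these endpoints, so no new data are required. No clinical rule or other analysis changes.
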